11.5.3 Pharmacokinetics

CDZ173 plasma concentration data will be listed by treatment, patient, and visit/sampling time point. Descriptive summary statistics will be provided by treatment and visit/sampling time point. Commercially Confidential Information Summary statistics will include mean (arithmetic and geometric), SD, CV (arithmetic and geometric), median, minimum and maximum. Commercially Confidential Information

A geometric mean will not be reported if the dataset includes zero values.

Pharmacokinetic parameters will be calculated as described in [Section 8.5](#) and will be listed by treatment and subject. Summary statistics will include mean (arithmetic and geometric), SD, CV (arithmetic and geometric), median, minimum and maximum. An exception to this is Tmax where median, minimum and maximum will be presented.

11.5.4 Pharmacokinetic / pharmacodynamic interactions

Relationships between exposure and selected PD or biomarker variables will be explored by a graphical approach and descriptive statistics of exposure and PD or biomarker variables will be provided. Additional analysis such as exposure-response models will be performed, if warranted.

11.5.5 Other assessments

11.5.5.1 Exploratory biomarkers

Commercially Confidential Information

Commercially Confidential Information

11.6 Sample size calculation

In Part I

The sample size for Part I (6 patients) was mainly based on feasibility, while still providing adequate precision to identify an appropriate dose for Part II.

Commercially Confidential Information

In Part II

For Part II, the sample size (20 patients in active and 10 patients in placebo for a total of 30 patients) is mostly driven by the analysis of one of the two co-primary efficacy variables, the change from baseline in the log10-transformed SPD of index lesions.

Commercially Confidential Information

Assuming that 10% of patients are excluded from the analysis of the other co-primary variable, the change from baseline in the percentage of naïve B cells out of total B cells, due to no reduced percentage of naïve B cells at baseline, it is anticipated that 27 patients will provide data for the analysis. Assuming an increase of 25% points and comparable variability as in Part I for the change from baseline to 12 weeks in the percentage of naïve B cells (standard deviation of 14), with 27 patients this part of the study will have 98% power to detect a statistically significant p-value at the 5% level.

With the above assumptions, the power to achieve a statistical significance in both endpoints is at least 78%.

11.7 Power for analysis of key secondary variables

Not applicable.

11.8 Interim analyses

Commercially Confidential Information

12 Ethical considerations

12.1 Regulatory and ethical compliance

This clinical study was designed and shall be implemented and reported in accordance with the ICH Harmonized Tripartite Guidelines for Good Clinical Practice, with applicable local regulations (including European Directive 2001/20/EC, US Code of Federal Regulations Title 21, and Japanese Ministry of Health, Labor, and Welfare), and with the ethical principles laid down in the Declaration of Helsinki.

12.2 Responsibilities of the investigator and IRB/IEC

Before initiating a trial, the Investigator/institution should obtain approval/favorable opinion from the Institutional Review Board/Independent Ethics Committee (IRB/IEC) for the trial protocol, written informed consent form, consent form updates, patient recruitment procedures (e.g. advertisements) and any other written information to be provided to patients. Prior to study start, the Investigator is required to sign a protocol signature page confirming his/her agreement to conduct the study in accordance with these documents and all of the instructions and procedures found in this protocol and to give access to all relevant data and records to Novartis monitors, auditors, Novartis Quality Assurance representatives, designated agents of Novartis, IRBs/IECs, and regulatory authorities as required. If an inspection of the clinical site is requested by a regulatory authority, the Investigator must inform Novartis immediately that this request has been made.

For multi-center trials, a Coordinating Investigator will be selected by Novartis around the time of Last Patient Last Visit to be a reviewer and signatory for the clinical study report.

12.3 Publication of study protocol and results

Novartis assures that the key design elements of this protocol will be posted in a publicly accessible database such as clinicaltrials.gov. In addition, upon study completion and finalization of the study report the results of this trial will be either submitted for publication and/or posted in a publicly accessible database of clinical trial results.

13 Protocol adherence

This protocol defines the study objectives, the study procedures and the data to be collected on study participants. Additional assessments required to ensure safety of subjects should be administered as deemed necessary on a case by case basis. Under no circumstances should an Investigator collect additional data or conduct any additional procedures for any research related purpose involving any investigational drugs.

Investigators must apply due diligence to avoid protocol deviations. If the Investigator feels a protocol deviation would improve the conduct of the study this must be considered a protocol amendment, and unless such an amendment is agreed upon by Novartis and approved by the IRB/IEC/REB it cannot be implemented. All significant protocol deviations will be recorded and reported in the CSR.

1.1 Scope

The RAP documents contain detailed information to aid the production of Statistics & Programming input into the Clinical Study Report (CSR) of trial “CCDZ173X2201”. This document describes the analyses for Part I.

Module 3 (M3) provides the description of the statistical methodology used to analyze the data, **Module 7 (M7)** details the presentation of the data, including shells of summary tables, figures and listings, and **Module 8 (M8)** contains programming specifications e.g. for derived variables and derived datasets, to support the creation of CSR outputs.

1.2 Changes to RAP documentation (M3)

Commercially Confidential Information

2 Study objectives and design

This study is designed to explore CDZ173, a selective PI3K δ inhibitor, in patients with genetically activated PI3K δ , i.e., patients with APDS/PASLI. The study consists of two parts. Part I is the open label part designed to establish the safety and pharmacokinetics of CDZ173 in the target population, as well as to select the optimal dose to be tested in Part II. Part II is designed to assess efficacy and safety of CDZ173 in this population.

This RAP focuses on Part I only.

2.1 Study objectives

2.1.1 Part I

2.1.1.1 Primary Objectives

- To assess the safety and tolerability of CDZ173 in patients with APDS/PASLI
- To assess the dose-PD and PK/PD relationship of CDZ173 in patients with APDS/PASLI for dose selection in Part II

2.1.1.2 Secondary Objectives

- To assess the pharmacokinetics of CDZ173 in patients with APDS/PASLI
- To assess the efficacy of CDZ173 to modify health-related quality of life in patients with APDS/PASLI
- To assess the efficacy of CDZ173 by the Physician's Global Assessment (PGA) and the Patient's Global Assessment (PtGA)
- To assess biomarkers reflecting the efficacy of CDZ173 to reduce systemic inflammatory components of the disease
- To assess the treatment benefit to individual patients

2.1.1.3 Exploratory Objectives

Commercially Confidential Information

2.2 Study design and treatment

2.2.1 Part I

Part I of the study will be the non-randomized, open-label, within-patient up-titration dose-finding part in approximately 6 patients with APDS/PASLI. Safety, tolerability, pharmacokinetics (PK) and in vivo pharmacodynamics (PD pAkt) will be assessed at three different dose levels of CDZ173. The starting dose is 10 mg followed by 30 mg and 70 mg b.i.d. for 4 weeks at each dose level respectively.

During the Screening Visit (Day -50 to Day -2) patients' eligibility will be assessed and then reviewed during the Baseline Visit. During this phase patients will be assessed for the following: Safety assessments which will include physical examinations, vital signs, standard clinical laboratory evaluations (hematology, blood chemistry, and urinalysis), adverse event and serious adverse event monitoring and cardiac safety which will be monitored by means of triplicate 12-lead electrocardiograms (ECG). Further assessments will include an MRI or CT scan, SF-36 and WPAI questionnaires and patient global assessment.

Patients who are deemed eligible for enrollment into the study based on the inclusion/exclusion criteria will attend the clinic on Day -1 for baseline assessments which include vital signs, ECG and PD blood collection.

The first day of dosing will start on Day 1 with patients receiving 10 mg of CDZ173 b.i.d.

Commercially Confidential Information Prior to escalation of a patient to the next dose level a continuous safety review and review of PK and key PD data up to 7 days after the first dose (Day 8) must be assessed as satisfactory to proceed with next dose level.

Commercially Confidential Information

[figure not shown]
The final dose strength that patients will be receiving is 70 mg CDZ173 b.i.d. Assessments done on Day 84 will include the end of treatment MRI or CT scan.

CCCI

During the four weeks after the last day of dosing the patients will be followed-up for safety. On Day 112 patients will undergo the end of study visit. Patients who are withdrawn from the study prematurely will still be required to complete the follow-up period including the Study Completion Visit.

Figure 2-1 illustrates the study design for Part I.

Figure 2-1 Study Design Part I

3 First interpretable results (FIR)

Commercially Confidential Information

4 Interim analyses

Commercially Confidential Information

5 Statistical methods: Analysis sets

For all analysis sets, patients will be analyzed according to the study treatment(s) received.

The safety analysis set will include all patients that received study drug and with no protocol deviations with relevant impact on safety.

The PK analysis set will include all patients with at least one available valid (i.e. not flagged for exclusion) PK concentration measurement, who received any study drug and experienced no protocol deviations with relevant impact on PK data.

The PD analysis set will include all patients with any available PD data, who received any study drug and experienced no protocol deviations with relevant impact on PD data.

Although the study includes both pediatric and adult patients, no separate analysis by age group (>18 years, ≤18 years) will be provided due to the small sample size. Listings will be provided by age group.

The analysis sets and protocol deviation codes are related as follows:

Table 5-1 Protocol deviation codes and analysis sets

Category Deviation code	Text description of deviation	Data exclusion
Subjects are excluded from all (safety) analysis in case of these PDs:		
INCL01	Written informed consent was not obtained before any study assessment was performed	Exclude subject completely from all (safety) analysis sets Yes
Subjects are excluded from PK analysis in case of these PDs:		Exclude subject from PK analysis set
INCL01	Written informed consent was not obtained before any study assessment was performed	Yes

Category Deviation code	Text description of deviation	Data exclusion
Subjects are excluded from PD analysis in case of these PDs:		Exclude subject from PD analysis set
INCL01	Written informed consent was not obtained before any study assessment was performed	Yes
Subjects are excluded from PK and PD analysis in case of these PDs:		Exclude subject from PK and PD analysis sets
INCL01	Written informed consent was not obtained before any study assessment was performed	Yes

6 Statistical methods for Pharmacokinetic (PK) parameters

6.1 Pharmacokinetic parameters

The following plasma pharmacokinetic parameters will be determined using the actual recorded sampling times and non-compartmental method(s) with Phoenix WinNonlin (Version 6.2 or higher): Cmax, Tmax and AUClast. Other PK parameters, including but not limited to AUCinf, CL(ss)/F and Cmax may be added as appropriate.

The linear trapezoidal rule will be used for AUC calculation. Regression analysis of the terminal plasma elimination phase for the determination of T1/2 will include at least 3 data points after Cmax. If the adjusted R² value of the regression analysis of the terminal phase will be less than 0.75, no values will be reported for T1/2, AUCinf and CL/F.

In addition to non-compartmental methods, individual compartmental modelling (Phoenix WinNonlin, version 6.2 or higher) may be used to derive individual estimates of oral drug clearance (CLss/F) as well other model-derived parameters such as absorption rate constant and volume of distribution.

6.2 Statistical methods for pharmacokinetic parameters

CDZ173 plasma concentration data will be listed by treatment, patient, and visit/sampling time point.

Descriptive summary statistics will be provided by treatment and visit/sampling time point,

Commercially Confidential Information Summary statistics will include mean (arithmetic and geometric), SD, CV (arithmetic and geometric), median, minimum and maximum. An exception to this is Tmax where median, minimum and maximum will be presented.

Commercially Confidential Information
if the dataset includes zero values.

A geometric mean will not be reported

Pharmacokinetic parameters will be calculated and will be listed by treatment and patient. Summary statistics will include mean (arithmetic and geometric), SD, CV (arithmetic and geometric), median, minimum and maximum. An exception to this is Tmax where median, minimum and maximum will be presented.

6.3 Pharmacokinetic / pharmacodynamic interactions

Relationships between exposure (plasma concentration and PK parameters) and pAkt PD biomarkers in B and T cells (endogenous, stimulated and unstimulated), will be explored by a graphical approach and descriptive

statistics of exposure and PD or biomarker variables will be provided.

Commercially Confidential Information

7 Statistical methods for Pharmacodynamic (PD) parameters

7.1 Primary Objective

The primary aim of Part I, along with assessing safety and tolerability, is to determine a dose to be used in the confirmatory Part II.

7.1.1 PD Variable(s)

Commercially Confidential Information

The primary parameter in Part I will be % pAkt positive B cells (unstimulated and stimulated samples) and will be used as PD marker to select the dose for Part II.

In Part I, phosphorylated Akt in B cells will be quantified at baseline and at Day 1 (pre-dose, and 1h, 3h, 8h post dose), Day 8 (pre-dose) and Day 15 (pre-dose) of each of the three dose levels and at Day 28 (pre-dose) of the last dose level. The dose level (up to 70 mg b.i.d.) leading to normalization of pAkt in B cells similar to healthy volunteer levels should be carried into Part II for generation of confirmatory data. Typically, pAkt levels in endogenous B-cells of healthy volunteers are not measurable due to limitation in detecting low levels of pAkt in these cells. Therefore, an integrated pharmacology approach consisting of the concentration/dose-effect relationship in inhibition of pAkt (unstimulated and stimulated B cells), as well as an estimate of the endogenous pAkt levels in APDS patients (if measurable) will be used to inform the best estimate of the level of inhibition required for normalization. Other variables including but not necessarily limited to safety and biomarkers will be taken into account for the selection of the dose.

Average pAkt inhibition (defined as $(-1) * \% \text{change from baseline}$) over the dosing interval of 12h will be calculated for each patient at each dose level based on the measured pre-dose and the 1h, 3h, 8h post dose samples with a trapezoidal rule as AUC over 12 hours normalized by the length of the dosing interval (12h). Baseline will be defined as the arithmetic mean of the Day -1 value and the first dose level Day 1 pre-dose value. The 12h time point will be estimated as an arithmetic mean of the Day 8 and Day 15 pre-dose values.

7.1.2 Statistical analysis of PD parameter(s)

7.1.2.1 Concentration-response (Plasma concentration vs PD parameter)

In Part I, a concentration-response model will be fitted to link systemic drug concentration and pAkt inhibition at each measured time point (the 1h, 3h, 8h post dose samples on Day 1 and pre-dose samples on Days 8 and 15 of each dose level; pre-dose samples on Day 1 of dose levels 2 and 3; and pre-dose sample on Day 28 of dose level 3). An Emax model will be considered, where the inhibition at concentration 0 is fixed at 0. The EC50, the Emax and the Hill parameter will be estimated from the data, and a random effect for EC50 and Emax will be estimated for each patient to account for the within-patient correlation between time points. Population model parameters will be converted into their dose equivalents based on desired time-averaged pathway inhibition and estimated oral drug clearance of CDZ173 in the target population.

The systemic drug concentrations used within the model will be the raw plasma concentrations measured at the same time points that the PD parameters were measured.

For the assessment of concentration-response, the following Emax model will be used:

$$Y_{ij} = \left(\frac{E_{max} \cdot C_{ij}^h}{EC_{50}^h + C_{ij}^h} \right) + e_{ij}$$

Y_{ij} : pAkt inhibition ((-1)*percent change from baseline) of the i -th patient at time point $j=1, \dots, 18$

C_{ij} : Concentration (ng/mL) of the i -th patient at time point $j=1, \dots, 18$

E_{max} : Maximum effect, logit transformed (between 0 and 100) = $100 / (1 + \exp(-\Theta_1))$

EC_{50} : Concentration (ng/nL) at which 50% of E_{max} is reached, log transformed $\exp(\Theta_2)$

h : Hill parameter, log transformed $\exp(\Theta_3)$

e_{ij} : residual error normally distributed

Random effects with multivariate normal distributions on transformed parameters ($\Theta_1, \Theta_2, \Theta_3$) will be estimated for each patient to account for the within-subject correlation between time points using a full covariance matrix. In case of estimation issues, a diagonal covariance matrix (i.e. off-diagonal elements are zero) will be used. In case there are still estimation issues, the below steps will be successively taken until there are no estimation issues. For each step, first a full covariance matrix will be used and in case of estimation issues, a diagonal covariance matrix will be used.

1. The random effect from the Hill parameter will be removed
2. The Hill parameter will be fixed to 1
3. The random effect on E_{max} will be removed
4. The random effect on EC_{50} will be removed

Commercially Confidential Information

Comercially Confidential Information

The dose D_{xx} (mg) that provides a given level (xx % of E_{max}) of time-averaged pathway inhibition over a dosing period (12h) is defined as follows:

$$D_{xx} = 10^{-3} \cdot EC_{xx} \cdot \frac{CL(ss)}{F} \cdot 12$$

$CL(ss)/F$: apparent Clearance (L/h)

EC_{xx} : Concentration (ng/mL) at which XX % of E_{max} is reached i.e. $\left(\frac{XX}{100-XX}\right)^{1/h} \times EC_{50}$ where h is the Hill parameter and EC_{50} the concentration at which 50% of E_{max} is reached.

To estimate EC_{xx} , the value $CL(ss)/F$ estimated from the pharmacokinetics assessment (see section 6.1) will be used.

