1.2 Data from Study Part I

Six APDS/PASLI patients completed study Part I of the present protocol (amendment #8). CDZ173 was found safe and well tolerated at all three dose levels. There were no SAEs and no premature treatment discontinuations due to AEs. In summary, 12 week treatment with CDZ173 led to significant improvements in the clinical presentation of the patients, including regression of lymph nodes and decrease in spleen size, naïve B cell numbers normalization, decrease of elevated transitional B cell numbers, reduction of senescent CD4+ and CD8+ T cells, reduction of elevated serum chemokines and suppression of the PI3K/Akt pathway activity. Mean oral plasma clearance at steady-state in the APDS patients was found to be 3.8 L/h, a value in close agreement to that seen in healthy volunteers. Also, no relevant time-dependencies or deviations from dose-proportionality were evident.

For further details of results please refer to the Clinical Study Report.

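### The Part I SAP's D_xx formula gives the dose whose average concentration equals EC_xx, which is not the time-averaged inhibition that its label names

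*SAP*

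**What the plan says.** Section 7.1.2.1 of the Part I SAP fits an Emax model with a Hill exponent to pAkt inhibition against concentration. The pairs are same-time values: "The systemic drug concentrations used within the model will be the raw plasma concentrations measured at the same time points" as the PD readings. The exponent is left to the data ("The EC50, the Emax and the Hill parameter will be estimated from the data"). If estimation fails, the second fallback step reads "The Hill parameter will be fixed to 1".

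The fitted parameters are then to be "converted into their dose equivalents based on desired time-averaged pathway inhibition and estimated oral drug clearance of CDZ173". Protocol 11.4.2 repeats this conversion. D_xx is the dose giving a chosen level, in percent of Emax, "of time-averaged pathway inhibition over a dosing period (12h) is defined as follows": 0.001 × EC_xx × CL(ss)/F × 12. EC_xx is the "Concentration (ng/mL) at which XX % of E_{max} is reached", that is (xx/(100 − xx))^(1/h) × EC50.

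Two neighbouring sections bear on this:

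- SAP 7.1.1 defines average inhibition over the dosing interval as the area under the inhibition curve over 12 h, divided by 12 h.
- SAP 7.1.2.2 fits a second Emax model (Hill fixed at 1) to that average inhibition against dose. It defines D_xx again with the same target description, as (xx/(100 − xx)) × ED50.

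**The concern.** The label promises an average of inhibition. The formula uses clearance and one point on the concentration-response curve, so it can control only the average of concentration. A saturating curve averaged over a fluctuating concentration does not equal the curve at the average concentration. Nothing in the formula reflects peak-to-trough fluctuation.

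The dose-PD and PK/PD relationship is a primary objective of Part I, and D_xx is one way in which the plan expresses it. A reader given a D_80 from 7.1.2.1 would take it to deliver 80% of Emax on average over 12 h, and in general it does not. A reader who sets it beside the D_80 from 7.1.2.2 would be comparing two different quantities under one name.

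**Working it through.** The documents give no numerical D_xx, EC50, Hill value or target xx, so there is no stated figure to reproduce. The check is of the formula itself.

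**1. What the formula returns.** At steady state, Cav = Dose / ((CL/F) × 12). Setting Cav = EC_xx gives Dose = EC_xx × CL/F × 12. Units: ng/mL is µg/L, and µg/L × L/h × h = µg, which the factor 0.001 turns into mg. This is the SAP formula exactly. Numerical check with Protocol 1.2 ("Mean oral plasma clearance at steady-state in the APDS patients was found to be 3.8 L/h"): 70 mg b.i.d. gives Cav = 70,000 / (3.8 × 12) = 1535.1 ng/mL, and 0.001 × 1535.1 × 3.8 × 12 = 70.0 mg.

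**2. Why that is not average inhibition.** Take h = 1 and xx = 80, so EC_80 = 4 × EC50. Suppose, for illustration only, that concentration is 6 × EC50 for half the interval and 2 × EC50 for the other half. The average is 4 × EC50, as the formula requires. Inhibition is 6/7 = 85.7% and 2/3 = 66.7% of Emax, which averages 76.2%, not 80%.

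**3. Direction.** Write E(C) = C^h / (EC50^h + C^h).

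- For h ≤ 1 the curve is concave. By Jensen's inequality the average of E(C) is at most E(Cav) = xx%, and is below it unless C is constant.
- For h > 1 the curve is sigmoid, with slope h × E × (1 − E) / C. The tangent passes through the origin where the slope equals E/C, that is h(1 − E) = 1, or E = 1 − 1/h. At or above that point the tangent lies on or above the whole curve, so the shortfall is again guaranteed. The condition is xx ≥ 100(1 − 1/h): 50% for h = 2, 67% for h = 3. In 20,000 random profiles there was no violation.
- For h > 1 below that threshold, the sign depends on the profile.

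**4. Size, under assumptions.** Assumed, and not in the documents: one compartment with first-order absorption, ka = 1.5/h, half-life 3 to 10 h. With k = ln 2 / half-life, the steady-state profile is proportional to e^(−kt)/(1 − e^(−12k)) − e^(−ka·t)/(1 − e^(−12ka)). It was scaled so that Cav = EC_xx, and E(C(t)) was averaged over 0 to 12 h. CL/F and EC50 cancel. In brackets is the ratio of the dose that solves the stated definition to the formula dose.

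| Half-life | D_80, h = 1 | D_80, h = 2 | D_90, h = 1 | D_90, h = 2 |
|---|---|---|---|---|
| 3 h | 74.0% (1.45) | 66.0% (1.64) | 85.8% (1.53) | 77.7% (1.80) |
| 5 h | 77.8% (1.14) | 74.3% (1.20) | 88.6% (1.16) | 85.7% (1.24) |
| 7 h | 78.9% (1.07) | 77.0% (1.10) | 89.3% (1.08) | 87.9% (1.12) |
| 10 h | 79.5% (1.03) | 78.5% (1.05) | 89.7% (1.04) | 89.0% (1.06) |

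The reversal is real but small here: with h = 2 and xx = 20, the formula dose gives 21.0% at a 3 h half-life and 20.1% at 10 h.

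**5. The second D_xx.** In 7.1.2.2 the response variable is already the 12 h average of inhibition, so its D_xx needs no step from Cav to average inhibition. The two definitions share a label but would coincide in general only for a flat profile.

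**The case against.** Four points can be made for the plan.

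- **D_xx did not decide the dose alone.** SAP 7.1.1 and 7.1.2.2 bring in stimulated and unstimulated pAkt, safety and other biomarkers, and 7.1.2.2 already models average inhibition directly. This stands. A reader might infer that the formula led to too low a dose in Part II, but the documents do not support that. Selection was capped at 70 mg b.i.d., and Part II uses 70 mg b.i.d. (Protocol 3.2.2). An understated D_xx could only have argued for less than the cap.
- **The formula does not always understate.** A reader might infer a universal downward bias. With h estimated and xx left open, that is not so, as step 3 shows. The plan aims at normalized or undetectable pAkt, which makes high targets the likely case, but the SAP fixes no value.
- **The size is assumed.** Half-life, ka, h and xx are not in the documents, and the largest figures come from the 3 h half-life. At 5 to 10 h the dose ratios are 1.03 to 1.16 (h = 1) and 1.05 to 1.24 (h = 2). The documented clearance cancels and lends no support to the size. This stands.
- **Redaction.** Text just before the definition is blacked out, so it cannot be known whether the formula was called an approximation there. The visible definition still attaches the label to the formula.

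None of these removes the mismatch between label and formula.

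**Conclusion.** The definition in SAP 7.1.2.1 is wrong as written: the formula gives the dose with Cav = EC_xx, and its label names average inhibition over 12 h. This is an identity and needs no assumption. Average inhibition at the formula dose is below xx% when h ≤ 1, which includes the SAP's own fallback, or when xx ≥ 100(1 − 1/h). Outside those conditions the direction is open.

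The size ranges from trivial to material, and the documents cannot say which. Under the assumptions in step 4, D_90 delivers 85.8 to 89.7% (h = 1) or 77.7 to 89.0% (h = 2).

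The consequence is limited to the meaning of a Part I dose-PD result and its consistency with the second D_xx in 7.1.2.2. No effect on the Part II dose is shown, and no view is taken on which dose is right.

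**What to change.** Reconcile the D_xx definitions in SAP 7.1.2.1 and 7.1.2.2, and carry the wording into Protocol 11.4.2 and any report of D_xx. Either of two changes is enough for 7.1.2.1:

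1. **Relabel.** Keep the formula, call the result the dose giving an average concentration of EC_xx, and stop describing it as time-averaged inhibition. This costs only wording.
2. **Redefine.** For each dose, average the fitted Emax curve over the predicted steady-state 12 h concentration profile, and let D_xx be the dose at which that average equals xx% of Emax. The numerical integration is short and needs no new data. It does require a commitment to the individual compartmental fits that SAP 6.1 only permits. D_xx then depends on those fits, in six patients, and not on clearance alone.

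Under either option, give the 7.1.2.1 and 7.1.2.2 quantities different names, or state how they are expected to relate.
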